1.1.6 Follow-up Data

The evidence for mammographic follow-up for invasive breast cancer and DCIS is limited. A Health Technology Assessment (HTA) sponsored meta-analysis (31) showed that follow-up regimens that included regular mammograms offer a survival benefit over those that did not. How long follow-up should continue is still subject to debate (21) and there are widespread differences in UK practice (32). However, given that the DCIS treatment and observational trials (23) all show that events continue to occur long term it would seem appropriate to continue active monitoring with annual mammography for at least 10 years before entering back into the NHSBSP.

1.1.7 Translational Science

A huge diversity of biological variation in invasive cancers is recognised but for DCIS is largely restricted to small studies of 'conventional markers' of invasive disease. There are an ever-increasing number of potential 'biomarkers' for invasive cancers but translational research into DCIS lags significantly behind. Categorisation of DCIS is routinely based predominantly on cytonuclear grade. The validity of grading of DCIS is reinforced by studies of biological markers; high grade DCIS is often positive for Human Epidermal Growth Factor Receptor 2 (HER-2) and p53 and tends to be negative for oestrogen receptor (ER), Progesterone Receptor (PgR) and bcl-2, with a high proliferation rate. Conversely, low grade DCIS is typically negative for HER-2 and p53, positive for ER, PgR and bcl-2, and has a low proliferation rate (33) (34). There are also genetic differences between different grades of DCIS indicating that these are truly different pathways to the progression of invasive carcinoma (35, 36). However, to date, none of these individual markers have proven efficacy in distinguishing between rates of recurrence, either of invasive or non-invasive disease. The processes involved in progression of DCIS to invasive disease are poorly understood. Most retrospective studies are under-powered and based on the premise that markers of prognosis in invasive cancer (e.g. HER-2, ER, Ki67) may predict recurrence in DCIS. Some evidence suggests these markers are prognostic in DCIS, however, until very recently, no reliable evidence existed to identify markers of invasive recurrence following an initial diagnosis of DCIS. There have been multiple challenges that act as barriers to effective and high quality translational research on DCIS. These include poor standardisation of pathology assessment, small samples, comparable fixation of all tissue for diagnosis, incomplete follow up, low event rates and lack of distinction between invasive versus DCIS recurrence in some of the published literature. Each of these, individually, restricts progress in this field. Within the LORIS trial, we are presented with a unique opportunity to surmount each of these obstacles, particularly when linked to advances in current technology that allow the analysis of gene expression from very small quantities of DNA/RNA (100-200ng) or from micro-dissected samples of 100-1000 cells.

The paucity of existing data on predictive biomarkers of invasion following a primary diagnosis of low risk DCIS makes it challenging to identify specific markers or marker panels which can be prospectively validated within the LORIS trial at present. However, experience has shown that progress in this field is rapid and the technological developments outlined above will provide impetus to this field.

Clearly, there is a need for research in this area to avoid inappropriately selecting DCIS cases with high risk of progression for observation rather than surgery. The biobanking of samples from the LORIS trial will provide a unique future resource for such studies and is regarded as an essential component of the study. By collecting samples for future analysis, we will secure a unique resource to allow such markers to be developed in future.

1.1.8 Psychosocial Aspects

The diagnosis of DCIS can provoke significant psychological distress; confusion about the seeming ambiguity of having "a very early form of breast cancer" with no manifest tumour, yet requiring treatments that may include mastectomy (37). Most published research is cross sectional comparing outcomes of women with DCIS and those with invasive breast cancer (9, 38).

Some research suggests that women treated for DCIS may have better physical, sexual, and social functioning than those with invasive breast cancer (32). However, despite the relatively good prognosis, one study showed that DCIS patients appeared to hold similar perceptions about the risks of recurrence and of dying as women with early invasive breast cancer. They also fear disease spreading to other parts of the body and these inaccurate perceptions changed little over 18 months (39, 40). At least two studies report psychological distress in DCIS to be similar to that found in women with invasive cancer (41).

Quality of Life (QoL) is a secondary outcome of the main trial and will provide unique insight and direction into the successful management of this condition.

Page 4 of 48 Version 4.0, 15th March 2016

1.2 Trial Rationale

1.2.1 Justification for Patient Population

The patient population are women of NHSBSP age or above (as these women can still access the screening programme) who have had their asymptomatic DCIS detected by mammogram. Outside of this age group, mammograms in the absence of symptoms are rarely performed and, consequently, the diagnosis of low and intermediate grade DCIS is also rare. Patients with high grade DCIS are excluded from this trial.

Men are not screened for breast cancer, very rarely have mammograms and are rarely diagnosed with DCIS.

To include patients diagnosed locally as having Atypical Ductal Hyperplasia or similar would potentially over-treat a population that is not currently being over-treated. However, if the local pathologist has reported a case as low grade DCIS and the Central Histopathology Reviewers deem the sample to represent ADH or similar the patient will still be considered eligible for randomisation. This pragmatism is required to ensure that the trial reflects current clinical practice. The only patients that the central review process will exclude are those with high risk disease.

To include low grade screen-detected invasive disease in this initial trial design is a step further than the wider surgical community might currently be prepared to accept.

1.2.2 Justification for Design

It is appropriate to address the issue of overtreatment of DCIS through a prospective randomised trial. Data from trials which have addressed the need for radiotherapy following breast conservation treatment do not contain many patients with low grade DCIS diagnosed with large volume biopsy, but do suggest that if low grade DCIS recurs as invasive cancer the cancer is also low grade and occurs much later than recurrence related to high grade DCIS e.g. NSABP-B17 (23). There is widespread concern amongst patient representative groups that the question of which women with DCIS diagnoses can safely avoid surgery is not being addressed within a contemporary prospective clinical trial and informed choice is therefore not currently possible. There is similar concern amongst many clinicians that adequate advice cannot be given to patients regarding overtreatment, as it has never been addressed. The clinical community has concentrated until now on discussing the degree of overtreatment

(e.g.www.breastcancercare.org.uk/forum/dcis-lcis-f21.html). There is no relevant, published QoL data to demonstrate the harms and/or benefits of current practice.

1.2.3 Choice of Treatment

The experimental arm of the LORIS trial is necessarily Active Monitoring alone, to answer the trial question of whether low risk DCIS is being overtreated, with healthy women undergoing unnecessary cancer treatment.

Page 5 of 48 Version 4.0, 15th March 2016

2 AIMS, OBJECTIVES AND OUTCOME MEASURES

2.1 Feasibility Study

2.1.1 Aims and Objectives

The aim of the Feasibility Study is to demonstrate that a sufficient number of eligible patients can be identified and recruited over the course of the main trial, in order to answer robustly the study objectives. This will be evaluated from the following factors:

- Number of sites open and randomising patients
- Number of patients randomised
- Mean monthly recruitment
- Identified patient conversion rate
- Number of patients with low or intermediate grade DCIS detected during screening for the LORIS
 Trial
- Patient consent to randomisation rate
- Concordance rate of DCIS grade between initial assessment and Central Histopathology Review

2.1.2 Outcome Measures

- Number of sites open and randomising patients: defined as the total number of sites activated for registration with at least 1 patient randomised at the end of year 2
- Number of patients randomised: total number of patients randomised from all randomising sites during the feasibility phase
- Mean monthly recruitment: defined as the average (mean) monthly number of patients randomised from all randomising sites involved in the Feasibility Study in total (not per site) during the final 4 months of the feasibility phase only (months 21-24)
- Identified patient conversion rate: defined as the number of randomised patients as a proportion of the number of patients identified as having low or intermediate grade DCIS and invited to take part during the final 4 months of the Feasibility Study only (months 21-24)
- Number of patients with low or intermediate grade DCIS detected during screening for the LORIS
 Trial: defined as the total number of patients with low or intermediate grade DCIS identified through
 Patient Screening/Enrolment Logs over the course of the Feasibility Study for all sites
- Patient consent to randomisation rate: defined as the percentage of patients consenting to randomisation during the Feasibility Study as a proportion of all patients identified as eligible for randomisation from Central Histopathology Review
- Concordance rate of DCIS grade between initial assessment and Central Histopathology Review: defined as the number of patients whose initial assessment of low or intermediate grade DCIS is confirmed by Central Histopathology Review, as a proportion of all samples reviewed during the Feasibility Study

Page 6 of 48 Version 4.0, 15th March 2016

2.2 Main Trial

2.2.1 Aims and Objectives

The aim of the main trial is to determine whether women with newly diagnosed low risk DCIS can safely avoid surgery, without detriment to their psychological well-being and can those patients who do require surgery be identified by pathological and radiological criteria.

2.2.1.1 Primary Objective

To assess whether Active Monitoring is non-inferior to Surgery, in terms of ipsilateral invasive breast cancer free survival.

2.2.1.2 Secondary Objectives

- Time to development of ipsilateral invasive breast cancer
- Time to development of any invasive breast cancer
- Time to development of contralateral invasive breast cancer
- Overall survival
- Time to mastectomy
- Time to surgery
- Quality of Life
- Quality-Adjusted Life Years (QALY)
- Costs and cost-utility

2.2.1.3 Translational Objectives

An exploratory assessment of predictive biomarkers will be performed

2.2.2 Outcome Measures of Main Trial

2.2.2.1 Primary Outcome

Ipsilateral invasive breast cancer free survival time: defined in whole days measured as time from randomisation until first report of ipsilateral invasive breast cancer or death (from any cause), whichever happens first. Patients who withdraw or who are lost to follow-up will be censored at the date last known to be alive and free of disease. Patients not having an event at the time of analysis will be censored at the date last seen alive and free of disease.

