7.1.2 Treatment

7.1.2.1 Surgery

Patients randomised to the Surgery Arm should undergo appropriate surgery according to local guidelines. It is expected that patients will undergo surgery within 60 days of randomisation.

Data on all related surgical procedures will be collected on the CRF, this also includes data on immediate or delayed breast reconstruction.

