7.2.2 Treatment

7.2.2.1 Surgery

Patients in the Active Monitoring arm will not undergo primary surgery.

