7.2.3.3 Ipsilateral Mammographic Indications for Patient Recall

An increase in the number, or size, of the microcalcification in the index lesion should not prompt routine patient recall. Neither should changes in the appearances/morphology, as casting type microcalcification is known to become more prevalent with increasing size.

Mammographic changes that would warrant a recall to clinic for further investigations are:

- A new cluster of microcalcification which is not definitively benign, outwith the index lesion/quadrant or remote from the index lesion
- A new cluster of microcalcification, which is not definitively benign in the contralateral breast
- A new non-calcified lesion which is not definitively benign in either breast
- Developing asymmetry or mass around the index calcification

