13 DATA HANDLING AND RECORD KEEPING

13.1 Data Collection

The Case Report Form (CRF) will comprise the following forms:

Form	Summary of data recorded	Schedule for submission		
Eligibility Checklist	Confirmation of eligibility	As soon as possible after registration		
Registration	Patient details; confirmation of local diagnosis of non-high grade DCIS	As soon as possible after registration		
Randomisation	Patient contact details; details of stratification variables; intended surgery	As soon as possible after randomisation		
Baseline	Details of biopsy histology (with copy of diagnostic biopsy report), concomitant medications (HRT, endocrine therapy (current/planned), NSAIDs)	Within 1 month of randomisation		
Surgery	Details of type of surgery performed, pathology of the DCIS specimen and any invasive disease identified, adverse events	Thirty days following completion of planned surgery (ies)		
Additional Treatment	Details of any radiotherapy, endocrine therapy, chemotherapy administered and adverse events	As soon as possible following any additional treatment performed or commenced		
Additional Investigations	Details of any additional mammography, other imaging or other biopsies performed	As soon as possible following any additional imaging or biopsies.		
Annual Follow-up	Survival, outcome of annual mammogram and record of related interventions and referrals, concomitant medications (HRT, endocrine therapy, NSAIDs), persisting protocol related adverse effects, health resource usage	Within 1 month of patient annual mammogram or as soon as possible following investigations or treatment if indicated		
Withdrawal	Date of withdrawal, type of withdrawal	Immediately following patient's request		
Subsequent DCIS Report	Date subsequent DCIS confirmed, side and site of cancer, diagnostic method	As soon as possible following confirmation of subsequent DCIS		
Invasive Breast Cancer	Date invasive breast cancer confirmed, side and site of cancer, method of detection	As soon as possible following confirmation of invasive breast cancer		
New (or non-breast cancer) or Metastatic Cancer	Date cancer confirmed, side and site of cancer, method of detection, details of biopsy (if applicable) and treatment details	As soon as possible following confirmation of new or metastatic cancer		
Deviation	Date of deviation, type of deviation	Immediately upon discovering deviation		
Death	Date of death, details of death	Immediately upon notification of patient's death		

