16.2.6 Sample Size Justification

The sample size calculation is based on the primary outcome of ipsilateral invasive breast cancer survival time. The primary analysis will be a comparison of the ipsilateral invasive breast cancer free rate between the Active Monitoring arm and Surgery Arm using a log-rank test for non-inferiority. The justification for the sample size is explained below.

Taking into account all published 5 year recurrence rates post-surgery for low risk disease, excluding contralateral disease and ipsilateral *in situ* disease, the projected recurrence rate (ipsilateral invasive breast cancer rate) at 5 years in the Surgery Arm is 2.5%. There is no relevant published data on 5 year ipsilateral invasive cancer rate in non-operated asymptomatic mammogram-detected low risk DCIS diagnosed by VACB and centrally reviewed. We have therefore based our non-inferiority calculation on extrapolation from the surgical data, estimates of overtreatment and what is judged to be a clinically relevant non-inferiority margin.

Page **36** of **48** Version 4.0, 15th March 2016

The non-inferiority design aims to show that not treating low risk DCIS with surgery is no worse (than a given margin) than treating with surgery. The primary outcome is ipsilateral invasive breast cancer free survival time and we will use a log-rank test for non-inferiority to determine whether no surgery is as good as surgery in these low risk DCIS patients by comparing the survival distributions of the two treatment groups. Because of the directional nature of the hypothesis, this non-inferiority test is one-sided. Jung *et al.* (49) derived an asymptotically exact sample size formula for the non-inferiority log-rank test to give the number of patients required to reject the null hypothesis that no surgery is worse than surgery, based on a given level of power and significance, assuming exponential survival distributions for both treatment groups, uniform patient accrual during a specified accrual period and set number of events during a period of follow-up, uniform censoring and no loss to follow-up.

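### Invasive cancer found at the allocated operation is an almost immediate surgery-arm event but counts later under monitoring, and HR 2.02 is calibrated to a rate that leaves such findings out

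*Protocol*

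**What the plan says.** Protocol 2.2.2.1 defines the primary outcome as "time from randomisation until first report of ipsilateral invasive breast cancer" or death of any cause, if that comes sooner. It makes no exception for what the allocated operation itself reveals.

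On the surgery arm, 7.1.2.1 says: "It is expected that patients will undergo surgery within 60 days of randomisation". The operation therefore falls after the clock has started. The Surgery form listed in 13.1 records "pathology of the DCIS specimen and any invasive disease identified".

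On the monitoring arm, 7.2.2.1 says: "Patients in the Active Monitoring arm will not undergo primary surgery". Section 7.2.3.3 adds: "An increase in the number, or size, of the microcalcification in the index lesion should not prompt routine patient recall". A developing mass or asymmetry at the index site does lead to recall, and mammography is annual.

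The planning rate in 16.2.6 is introduced with the words "Taking into account all published 5 year recurrence rates post-surgery for low risk disease". That gives 2.5% at 5 years for the surgery arm. Sections 16.2.2 and 16.2.6 set the margin at 2.5 percentage points (97.5% to 95%) and convert it to a hazard ratio of 2.02. Section 16.2.2 tests it with a one-sided 5% log-rank test for non-inferiority and a one-sided 95% confidence interval for the hazard ratio.

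**The concern.** Randomisation should give both arms the same share of women whose biopsy missed an invasive focus. The surgery arm has all its specimens examined within weeks, so it registers these cancers at once. The monitoring arm registers them as they surface. Detection therefore differs by arm, by design.

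The margin is a separate problem. A recurrence after surgery cannot include invasion found at the surgery, so the 2.5% belongs to one event definition and the endpoint in 2.2.2.1 to another. A fixed hazard ratio allows a wider absolute gap as the control rate rises. The 2.5 points that 16.2.2 describes as clinically acceptable are then no longer what the test enforces.

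Both effects favour monitoring. The trial could support omitting surgery partly because cancers present at baseline were reported sooner in the surgery arm.

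**Working it through.** **1. The plan's own figures reproduce.**
- HR margin: ln(0.95) / ln(0.975) = 2.026; the protocol gives 2.02.
- Events (Schoenfeld, 1:1, one-sided 5%, 80% power): 4 × (1.645 + 0.842)² / (ln 2.026)² = 49.6, so 50.
- Patients: exponential survival at 97.5% and 95%, 6 years' uniform accrual and 5 years' further follow-up give a mean event probability of 5.92%. Then 49.6 / 0.0592 ≈ 839 evaluable, and 839 / 0.90 ≈ 933, against 932 stated.

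The sample-size arithmetic is sound for the rates that it uses.

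**2. Input that the protocol does not give.** Let *u* be the share of women with invasion missed by biopsy, the same in both arms. No figure is given. The assumed range is 0.5% to 5%.

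**3. What HR 2.02 allows in absolute terms.** The surgery-arm 5-year event-free proportion becomes S = (1 − u) × 0.975. HR 2.02 then permits S^2.02 under monitoring, a gap of S − S^2.02. For u = 0.5%: S = 0.995 × 0.975 = 0.9701; 0.9701^2.02 = 0.9406; gap 2.96 points.

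**4. Chance of declaring non-inferiority by the HR test when it is false.** This was simulated with later risk truly at the limit (5% v 2.5% at 5 years) and about 840 evaluable patients. Surgery-arm occult cancers are reported within 60 days. Monitoring-arm occult cancers surface after an exponential lag with mean 1 to 7 years. Deaths are not modelled.

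| u (assumed) | Surgery-arm 5-year risk | Gap allowed by HR 2.02 | False non-inferiority |
|---|---|---|---|
| 0 | 2.5% | 2.5 points | 5% |
| 0.5% | 3.0% | 3.0 points | 7–9% |
| 1% | 3.5% | 3.4 points | 10–14% |
| 2% | 4.5% | 4.3 points | 18–26% |
| 5% | 7.4% | 7.0 points | 49–72% |

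Small values of u matter because the surgery arm expects only about 17 events, and each 1% of upstaging adds about 419.5 × 0.01 ≈ 4.

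**5. Is it only a detection delay?** No. If every occult cancer surfaces under monitoring within 5 years, false non-inferiority is still about 11% at u = 1%, 20% at 2% and 50% at 5%. Disease common to both arms dilutes a ratio even when it is eventually found in both.

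**6. Does the absolute scale repair it?** Mostly. On the 5-year risk difference with a 1-year lag, the error is about 5% at u = 2% and 6% at u = 5%. With a 7-year lag it is about 15% and 40%.

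**7. Does dropping index-operation cancers repair it?** No, because that removes prevalent cancers from one arm only. With equal later risk (2.5% in both arms), the HR test concludes non-inferiority in about 65% of trials when there is no occult disease. With index cancers dropped, this falls to about 24–35% at u = 2%.

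**The case against.** Four counter-arguments have force.

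- **Monitoring-arm cancers do count.** A reader might infer that the occult cancer stays uncounted under monitoring. The documents do not support that. Any later report is an event under 2.2.2.1, mammography is annual for 10 years, a developing mass or asymmetry prompts recall, and every patient has at least 5 years' follow-up before the analysis. This reduces the bias but does not remove it (step 5).
- **The upstaging rate is assumed.** The protocol guards against missed invasion with vacuum biopsy of at least 12-gauge, six cores recommended for most patients, exclusion of unproven masses and of comedo necrosis, and at least two central pathologists. A reader might infer error rates above 90%; these arise in the lagged runs only at an assumed 10%, which nothing in the protocol supports. The size is therefore uncertain; the direction is the same in every scenario run.
- **Deaths are left out of the simulation.** Death from any cause is a primary event. The 5% baseline thus describes a simpler endpoint. Similar death rates in both arms would dilute the hazard ratio further towards 1.
- **The data are kept apart, and a SAP could set the handling.** Specimen invasion is on the Surgery form, and later cancers have their own dated form. But the endpoint definition, the test and the HR margin are fixed in the protocol, and none of them uses that distinction.

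**Conclusion.** The point stands as a mismatch inside the protocol. The endpoint counts invasion found at the allocated operation, while the 2.5% control rate and HR 2.02 come from a quantity that excludes it. Upstaging makes the HR test easier to pass and looser than the stated 2.5 points. The error at the limit rises from 5% to about 7–9% at an assumed 0.5% upstaging and to 18–26% at 2%.

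Confidence is high in the direction and limited in the size. The size rests on the assumed upstaging rate, equal prevalence in both arms, the assumed detection lag and the omission of deaths.

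Two further inferences are not supported. Shared disease does not simply cancel on the absolute scale; it does so nearly only when occult cancers surface well within 5 years. Nor is an analysis that drops index-operation cancers a fair deciding test, because it biases the comparison against monitoring.

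**What to change.** Amend 2.2.2.1 and 16.2.2, and carry the change into the SAP, before any comparative results are seen.

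1. State whether invasive cancer found at the allocated operation is a primary event, and classify it separately from later events using the Surgery form.
2. Require the conclusion to hold on the protocol's own 2.5-point absolute difference at 5 years, not on HR 2.02 alone. Acknowledge that this removes most but not all of the bias if occult cancers surface slowly. Restate power for that criterion. With equal later risk it is about 76% with no occult disease; with a 1-year lag it is about 55% at 2% occult disease and 40% at 5%.
3. Pre-specify sensitivity analyses that bound the result in both directions:
   - index-operation cancers counted;
   - index-operation cancers not counted, labelled as biased against monitoring and not as a deciding test;
   - prevalent disease treated alike in both arms, for example by varying the assumed share of monitoring-arm cancers that were present at baseline.

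The cost is wording, a power calculation and a few analyses on data already collected. The stated power will be less favourable, and the non-inferiority claim becomes harder to make.
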